7.1 Study Subjects

7.1.1 Disposition of Subjects

The number of subjects enrolled in the study will be presented by training period and study period. The reasons for discontinuing prior to study completion will be summarized.

7.1.2 Clinical Investigation Plan (CIP) Deviations

All protocol deviations will be presented in the listings.

7.1.3 Analysis Sets

All enrolled subjects who have at least one paired Guardian™ Sensor (3) and YSI™* measurement will be included in the efficacy analysis population. All enrolled subjects who have a Guardian™ Sensor (3) inserted will be included in the safety analysis population.

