## **Ages 2 - 6 years**

Subjects ages 2 – 6 years will only do SMBG during their FST. The fingerstick glucose values will be recorded on the appropriate eCRF and will be used for analysis.

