## 15.7. Assignment to Day of YSI™\* FST

Adult subjects and subjects with age of 14 - 80 will be required to attend four 8-hour sessions of frequent sampling in which agreement between YSI™\* and Guardian™ Sensor (3)s connected to the Guardian™ Connect Transmitters will be evaluated.

Pediatric subjects with age of 7 – 13 will be required to attend two 6-hour sessions of frequent sampling in which agreement between YSI™\* and Guardian™ Sensor (3)s connected to the Guardian™ Connect Transmitters will be evaluated.

Pediatric subjects with age of 2 – 6 will be required to attend two 4-hour sessions of frequent sampling in which agreement between SMBG and Guardian™ Sensor (3)s connected to the Guardian™ Connect Transmitters will be evaluated.

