### **15.8.2. Pairing Scheme**

All YSI™\* and fingerstick values collected will be presented. However, primary endpoint analysis will only include Guardian™ Sensor (3) values of 50-400 mg/dL and paired YSI™\*.

YSI™\* values will be paired with the closest Guardian™ Sensor (3) value between [0, 5) minutes. Fingerstick values that were not used for calibration will be paired with the closest Guardian™ Sensor (3) value within [0, 5) minutes.

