6.1 Guardian™ Sensor (3) accuracy, Threshold of 75%

The sample size selected is based on the primary effectiveness endpoint, which is the within 20% mean agreement rate (± 20 mg/dL when Reference BG less than ($<$) 80 mg/dL) in comparative readings of paired Guardian™ Sensor (3) and YSI™* glucose readings in FST days. On those 4 FST days, 8 hours of paired testing will be recorded.

Data from CIP318 and ERP2018-11254 study was used for power estimation via simulation.

The simulation was performed 1000 times and the 95% lower confidence limit of 75%. The results of the simulation indicated that a sample size of 122 will yield greater than 80% power.

7. Statistical Methods

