7.9 Evaluation of Objectives

7.9.1 Primary Endpoints

A total of 16 primary endpoints will be independently evaluated in blocks of 16 in the study. Analysis will be done in the blocks of 16 as:

- Adult (18 – 80 years), abdomen insertion location and 0 Calibration of Zeus algorithm
- Adult (18 – 80 years), abdomen insertion location and two Calibrations of Zeus algorithm (first calibration at 2 hours after insertion and second calibration at 8 hours after first calibration)
- Adult (18 – 80 years), abdomen insertion location and three Calibrations of Zeus algorithm (first calibration at 2 hours after insertion, second calibration at 8 hours after first calibration, and 14 hours after second calibration)
- Adult (18 – 80 years), abdomen insertion location and daily Calibrations of Zeus algorithm (first calibration at 2 hours after insertion, second calibration at 8 hours after first calibration, 14 hours after second calibration and 24 hours after the previous calibration until end of wear)
- Adult (18 – 80 years), arm insertion location and 0 Calibration of Zeus algorithm

- Adult (18 – 80 years), arm insertion location and two Calibrations of Zeus algorithm (first calibration at 2 hours after insertion and second calibration at 8 hours after first calibration)
- Adult (18 – 80 years), arm insertion location and three Calibrations of Zeus algorithm (first calibration at 2 hours after insertion, second calibration at 8 hours after first calibration, and 14 hours after second calibration)
- Adult (18 – 80 years), arm insertion location and daily Calibrations of Zeus algorithm (first calibration at 2 hours after insertion, second calibration at 8 hours after first calibration, 14 hours after second calibration and 24 hours after the previous calibration until end of wear)
- Peds (2 to 17 years), buttock insertion location and 0 Calibration of Zeus algorithm
- Peds (2 to 17 years), buttock insertion location and two Calibrations of Zeus algorithm (first calibration at 2 hours after insertion and second calibration at 8 hours after first calibration)
- Peds (2 to 17 years), buttock insertion location and three Calibrations of Zeus algorithm (first calibration at 2 hours after insertion, second calibration at 8 hours after first calibration, and 14 hours after second calibration)

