- Peds (2 to 17 years), buttock insertion location and daily Calibrations of Zeus algorithm (first calibration at 2 hours after insertion, second calibration at 8 hours after first calibration, 14 hours after second calibration and 24 hours after the previous calibration until end of wear)
- Peds (2 to 17 years), arm insertion location and 0 Calibration of Zeus algorithm
- Peds (2 to 17 years), arm insertion location and two Calibrations of Zeus algorithm (first calibration at 2 hours after insertion and second calibration at 8 hours after first calibration)
- Peds (2 to 17 years), arm insertion location and three Calibrations of Zeus algorithm (first calibration at 2 hours after insertion, second calibration at 8 hours after first calibration, and 14 hours after second calibration)
- Peds (2 to 17 years), arm insertion location and daily Calibrations of Zeus algorithm (first calibration at 2 hours after insertion, second calibration at 8 hours after first calibration, 14 hours after second calibration and 24 hours after the previous calibration until end of wear)

Guardian™ Sensor (3) accuracy for ZEUS Algorithms

- Guardian™ Sensor (3) values will be compared to YSI™* plasma glucose values during YSI™* FSTs. A within 20% mean agreement rate (± 20 mg/dL when SG less than ($<$) 80 mg/dL), μ , between Guardian™ Sensor (3) values and YSI™* plasma glucose values during YSI™* FST days will be evaluated against the null Hypothesis:

$H_0: \mu \leq 75\%$ $H_1: \mu > 75\%$

- Statistical testing

A generalized estimating equation method model will be used. The one sided 95% lower confidence limit of the mean agreement rate will be tested against the threshold of 75%. For the GEE model, Exchangable (exch) or Auto-regressive (AR1) or Independence (IND) correlation structure will be used, based on quasi-AIC (QIC). Confidence intervals from bias-corrected and accelerated percentile bootstrap approaches will be provided, if applicable. In addition, the confidence intervals from GEE model and bootstrap approaches will be adjusted based on the proposed alpha level at the interim analyses. Site effect will be evaluated. If it is not significant (p-value greater than ($>$) 0.1), site will not be included in the model so as to obtain the adjusted confidence limit.

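### The eight primary endpoints labelled ages 2–17 can contain only ages 7–17, and the N = 122 power is not shown for them

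*SAP*

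**What the plan says.** The objective in SAP 4 covers ages 2–80, and SAP 5 sets 122 completers aged 2–17. SAP 7.9.1 lists 16 primary endpoints. Eight are pediatric (arm or buttock, four calibration schemes each), for example "Peds (2 to 17 years), buttock insertion location and 0 Calibration of Zeus algorithm".

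Three rules decide whose data enter these endpoints, and each names YSI:

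- Analysis set (SAP 7.1.3, same as Protocol 15.6): "All enrolled subjects who have at least one paired Guardian™ Sensor (3) and YSI™* measurement will be included in the efficacy analysis population".
- Pairing (Protocol 15.8.2): "primary endpoint analysis will only include Guardian™ Sensor (3) values of 50-400 mg/dL and paired" YSI values.
- Endpoint (SAP 7.9.1): "Guardian™ Sensor (3) values will be compared to YSI™* plasma glucose values during YSI™* FSTs".

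For the youngest children Protocol 10.5.2 says: "Subjects ages 2 – 6 years will only do SMBG during their FST". Protocol 9.1 and 15.7 agree, and Protocol 9.2.2.6.2 limits YSI set-up and upload within the 2–13 group to ages 7–13.

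On sample size, SAP 6.1 says "On those 4 FST days, 8 hours of paired testing will be recorded" and "The results of the simulation indicated that a sample size of 122 will yield greater than 80% power". For ages 7–13, Protocol 15.7 says "Pediatric subjects with age of 7 – 13 will be required to attend two 6-hour sessions of frequent sampling". Ages 2–6 have two 4-hour sessions with SMBG as the reference.

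**The concern.** Followed as written, a pediatric primary endpoint can be met and reported as accuracy in ages 2–17 without one data point from ages 2–6. The label would not reveal this. The Protocol Synopsis (Devices) notes that ages 2–6 are the group in which the sensor itself is used outside its approved use, so this is the age range where a silent gap matters most in a pivotal study.

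The second issue is the sample size. The only power statement assumes 122 subjects with 32 hours of YSI pairing each. That schedule fits ages 14–80. In the pediatric cohort some subjects supply no YSI pairs and others supply 12 hours, so the stated power does not describe the pediatric endpoints.

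**Working it through.** **Who can enter the pediatric blocks.** Ages 2–6 have no YSI value, so they fail the analysis-set rule, the pairing rule and the endpoint definition in turn. No passage assigns SMBG to the primary endpoint. In each of the two secondary lists in SAP 7.9.2, 7 of 11 endpoints also name YSI, which is 14 of 22 per block. The other four in each list refer to blood glucose.

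**How many are affected (minima from SAP 5).**

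- Sum of minima: 15 + 15 + 20 + 20 + 24 = 94, so 122 − 94 = 28 places are unallocated.
- Ages 2–6: 30 (30/122 = 25%) up to 30 + 28 = 58 (58/122 = 48%).
- Completers able to supply YSI pairs: 122 − 58 = 64 up to 122 − 30 = 92. Every subject aged 7–17 wears a primary sensor at both sites, so this range applies to each pediatric block.

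**Scheduled YSI time.** The sample-size basis is 122 × 32 h = 3904 h. Against it:

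| 28 unallocated places go to | Hours | Share of 3904 |
|---|---|---|
| Ages 2–6 | 40×12 + 24×32 = 1248 | 32% |
| Ages 7–13 | 68×12 + 24×32 = 1584 | 41% |
| Ages 14–17 | 40×12 + 52×32 = 2144 | 55% |

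**The plan's own power figure.** It cannot be reproduced. SAP 6.1 names two source studies but gives no assumed agreement rate, between-subject SD or within-subject correlation. Many inputs fit. With SD = (π − 0.75)√122 / (1.645 + 0.842), exactly 80% power at one-sided 0.05 corresponds to an SD of 0.133, 0.222, 0.311 or 0.444 for a true rate π of 78%, 80%, 82% or 85%.

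**Effect of fewer subjects, conditional on power at 122.** With equal information per subject,

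Power(n) = Φ[(z₁₋α + z_P122)·√(n/122) − z₁₋α], α = 0.05 one-sided.

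For P122 = 80%: at n = 92, Φ(2.486 × 0.868 − 1.645) = 0.697; at n = 64, Φ(2.486 × 0.724 − 1.645) = 0.562.

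| Assumed power at 122 | n = 92 | n = 64 |
|---|---|---|
| 80% | 0.697 | 0.562 |
| 90% | 0.815 | 0.682 |
| 95% | 0.887 | 0.770 |
| 99% | 0.964 | 0.891 |

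Solving backwards, 80% is kept if power at 122 was at least about 89% (n = 92) or 96% (n = 64). At the final-analysis threshold of 0.041, a starting 80% becomes 0.692 and 0.552.

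**Allowing for shorter sessions.** At one sample per 15 minutes, ages 14–17 give 4×8×4 = 128 pairs and ages 7–13 give 2×6×4 = 48. Under an exchangeable correlation ρ, the variance of the pooled rate is proportional to Σ n·m·[1 + (m−1)ρ] / (Σ n·m)², where n subjects give m pairs each. For assumed ρ from 0.05 to 0.3, the 64 to 92 subjects carry the information of about 49 to 78 subjects with 32 hours each. Power would then be 0.475 to 0.633 if it is 80% at 122, or 0.585 to 0.755 if it is 90%. The values of ρ are not from the documents.

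**The case against.** The documents do intend to compare sensor with SMBG in ages 2–6. The SAP background, Protocol 10.5.2 and Protocol 15.7 say so. Protocol 15.8.2 has a fingerstick pairing rule, SAP 7.9.10 describes fingerstick agreement under its home-use heading, and the alert rates in SAP 7.9.8 accept SMBG as reference. This stands: the gap is in primary evidence and in a defined analysis, not in all planned data. But none of these passages supplies an analysis set, endpoint or confidence interval for the 2–6 year in-clinic sessions, and SAP 7.9.4 ties the in-clinic difference tables to YSI.

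The power figures are scenarios. The plan claims more than 80%, the simulation may have been well above it, and whether it modelled the pediatric sessions is unknown. This also stands, so the claim is only that the power is not shown. The hours comparison alone overstates the loss, because repeated pairs within a subject are correlated.

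The 64 to 92 range counts completers, whereas the efficacy set takes any enrolled subject with a YSI pair, so non-completers could add some. The lower end needs all 28 spare places to go to ages 2–6. Both points soften the size but leave the mismatch.

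A coherent alternative would be to declare SMBG the primary reference for ages 2–6. That too requires rewriting all three rules, and it would pool two reference methods.

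**Conclusion.** The concern holds. As written, the eight pediatric primary endpoints labelled 2 to 17 years can contain only ages 7–17 and give no primary evidence for ages 2–6. This part follows from the text alone.

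The size, 30 to 58 of 122 pediatric completers without YSI data and 64 to 92 with it, rests on exactly 122 completers with all age minima met. The stated power is not shown for these endpoints. Whether it falls below 80% cannot be determined, and the power values above depend on an assumed power at 122 and, in the main table, on equal information per subject. The tests in ages 7–17 and 18–80 remain valid for those ages.

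**What to change.** 1. In SAP 7.9.1 and Protocol 4.2.1 and 15.9, relabel the eight pediatric blocks as 7 to 17 years and limit the primary conclusion to ages 7–80. Reconcile the 2–80 year objective with this.
2. In SAP 7.1.3 and Protocol 15.6, add a separate accuracy set for ages 2–6: at least one sensor–SMBG pair from an FST, with calibration fingersticks excluded under the existing rule in Protocol 15.8.2. Report within-20% agreement with a confidence interval, not pooled with YSI pairs because the reference method differs.
3. In SAP 6.1 and Protocol 15.5.1, restate pediatric power by rerunning the existing simulation at the expected number of YSI-contributing children, with 2 × 6 h for ages 7–13 and 4 × 8 h for ages 14–17.
4. In SAP 7.8 and Protocol 15.15, state whether the pediatric interim counts of 40 and 100 completers mean subjects with YSI data; at present they may include children without any.

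The cost is wording, one extra table from data already collected, and a rerun of an existing simulation. The primary claim becomes narrower, and the stated pediatric power may be less favourable.

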7.2 General Methodology

All data collected from the time of screening until the end of the study will be collected either on eCRFs or electronically by downloading the various devices. Data and analysis will be summarized in a Clinical Study Report.

7.3 Center Pooling

Data will be pooled per cohort for analysis.

7.4 Handling of Missing, Unused, and Spurious Data and Dropouts

All available data will be included in the data listings and tabulations. No imputation for missing data will be performed.

7.5 Adjustments for Multiple Comparisons

Secondary endpoints will be evaluated in a fixed sequence of testing for adjustment of multiplicity.

7.6 Demographic and Other Baseline Characteristics

Subject characteristics, including age, gender, race, ethnicity, medical diagnosis, height, weight, and BMI will be summarized by descriptive statistics (mean, standard deviation, minimum, median, and maximum) for continuous variables and by counts and percentages for categorical variables.

7.7 Treatment Characteristics

The number of Guardian™ Sensor (3) insertions and Guardian™ Sensor (3) removals for every subject enrolled in the study will be presented.

A descriptive analysis of Guardian™ Sensor (3) disposition including Guardian™ Sensor (3) dislodgement and reasons why it dislodged will be included in the Final Report. Guardian™ Sensor (3) insertion and removals will be characterized by the following:

- Guardian™ Sensor (3) location
- Duration of Guardian™ Sensor (3) wear by investigational center subject report
- The number and percentage of Guardian™ Sensor (3)s remaining in place at study end.
- Duration of Guardian™ Sensor (3) wear (subject report) by insertion site.
- Reason for removal: for example, scheduled removal, adverse event, fell out.

The functional life of the Guardian™ Sensor (3) will also be characterized. The duration of Guardian™ Sensor (3) performance from the time of first valid Interstitial Signal (ISIG) to the last glucose reading (i.e., time to end of Guardian™ Sensor (3) life) will be described with Kaplan-Meier curves.

7.8 Interim Analyses

Interim Analysis will be performed for primary effectiveness endpoint to provide direction for continuing enrollment. If primary endpoint is met, secondary endpoints will also be evaluated. Two interim analyses will be conducted after there are 40 and 100 adult subjects complete the study, and separate two interim analyses will be conducted after there are 40 and 100 pediatric subjects complete the study.

The standard group sequential O'Brien-Fleming's approach will be used to estimate of significance level at interim analysis.

Number of Planned Analyses	Number of Interim Analyses	Number of Subjects	P-value threshold (alpha)
3	1	40	N/A*
	2	100	0.031
	3 (final)	122	0.041

*N/A: No intention to stop for efficacy at the first interim analysis (N = 40). Therefore, p-value threshold (alpha) is Not Applicable (N/A)

For this three stage design, hypothesis testing (primary and secondary endpoints) will be conducted at $p = 0.031$ and $p = 0.041$ for the second (N = 100) and final analyses (N = 122), using O'Brien-Fleming's approach. If significance is found at the second interim analysis at N = 100 complete subject, Medtronic may request to stop the study because endpoints are met. Otherwise, the study will continue up to the planned enrollment.

7.9 Evaluation of Objectives

7.9.1 Primary Endpoints

A total of 16 primary endpoints will be independently evaluated in blocks of 16 in the study. Analysis will be done in the blocks of 16 as:

- Adult (18 – 80 years), abdomen insertion location and 0 Calibration of Zeus algorithm
- Adult (18 – 80 years), abdomen insertion location and two Calibrations of Zeus algorithm (first calibration at 2 hours after insertion and second calibration at 8 hours after first calibration)
- Adult (18 – 80 years), abdomen insertion location and three Calibrations of Zeus algorithm (first calibration at 2 hours after insertion, second calibration at 8 hours after first calibration, and 14 hours after second calibration)
- Adult (18 – 80 years), abdomen insertion location and daily Calibrations of Zeus algorithm (first calibration at 2 hours after insertion, second calibration at 8 hours after first calibration, 14 hours after second calibration and 24 hours after the previous calibration until end of wear)
- Adult (18 – 80 years), arm insertion location and 0 Calibration of Zeus algorithm

- Adult (18 – 80 years), arm insertion location and two Calibrations of Zeus algorithm (first calibration at 2 hours after insertion and second calibration at 8 hours after first calibration)
- Adult (18 – 80 years), arm insertion location and three Calibrations of Zeus algorithm (first calibration at 2 hours after insertion, second calibration at 8 hours after first calibration, and 14 hours after second calibration)
- Adult (18 – 80 years), arm insertion location and daily Calibrations of Zeus algorithm (first calibration at 2 hours after insertion, second calibration at 8 hours after first calibration, 14 hours after second calibration and 24 hours after the previous calibration until end of wear)
- Peds (2 to 17 years), buttock insertion location and 0 Calibration of Zeus algorithm
- Peds (2 to 17 years), buttock insertion location and two Calibrations of Zeus algorithm (first calibration at 2 hours after insertion and second calibration at 8 hours after first calibration)
- Peds (2 to 17 years), buttock insertion location and three Calibrations of Zeus algorithm (first calibration at 2 hours after insertion, second calibration at 8 hours after first calibration, and 14 hours after second calibration)
- Peds (2 to 17 years), buttock insertion location and daily Calibrations of Zeus algorithm (first calibration at 2 hours after insertion, second calibration at 8 hours after first calibration, 14 hours after second calibration and 24 hours after the previous calibration until end of wear)
- Peds (2 to 17 years), arm insertion location and 0 Calibration of Zeus algorithm
- Peds (2 to 17 years), arm insertion location and two Calibrations of Zeus algorithm (first calibration at 2 hours after insertion and second calibration at 8 hours after first calibration)
- Peds (2 to 17 years), arm insertion location and three Calibrations of Zeus algorithm (first calibration at 2 hours after insertion, second calibration at 8 hours after first calibration, and 14 hours after second calibration)
- Peds (2 to 17 years), arm insertion location and daily Calibrations of Zeus algorithm (first calibration at 2 hours after insertion, second calibration at 8 hours after first calibration, 14 hours after second calibration and 24 hours after the previous calibration until end of wear)

Guardian™ Sensor (3) accuracy for ZEUS Algorithms

- Guardian™ Sensor (3) values will be compared to YSI™* plasma glucose values during YSI™* FSTs. A within 20% mean agreement rate (± 20 mg/dL when SG less than ($<$) 80 mg/dL), μ , between Guardian™ Sensor (3) values and YSI™* plasma glucose values during YSI™* FST days will be evaluated against the null Hypothesis:

$H_0: \mu \leq 75\%$ $H_1: \mu > 75\%$

- Statistical testing

A generalized estimating equation method model will be used. The one sided 95% lower confidence limit of the mean agreement rate will be tested against the threshold of 75%. For the GEE model, Exchangable (exch) or Auto-regressive (AR1) or Independence (IND) correlation structure will be used, based on quasi-AIC (QIC). Confidence intervals from bias-corrected and accelerated percentile bootstrap approaches will be provided, if applicable. In addition, the confidence intervals from GEE model and bootstrap approaches will be adjusted based on the proposed alpha level at the interim analyses. Site effect will be evaluated. If it is not significant (p-value greater than ($>$) 0.1), site will not be included in the model so as to obtain the adjusted confidence limit.

7.9.2 Secondary Endpoints

Within each block of 16, secondary endpoints (a total of 176) will be evaluated in a fixed sequence of testing for adjustment of multiplicity. The results will be compared to the iCGM Special Control criteria for sensor accuracy (SG limit of **50-400** mg/dL). For each of the endpoints, iCGM measurement refers to the sensor glucose value:

- % of iCGM measurements that indicate a positive glucose rate of change greater than 1 mg/dL/min when the corresponding true negative glucose rate of change is less than -2 mg/dL/min as determined by the corresponding blood glucose measurements
- % of iCGM measurements that indicate a negative glucose rate of change less than -1 mg/dL/min when the corresponding true positive glucose rate of change is greater than 2 mg/dL/min as determined by the corresponding blood glucose measurements
- Guardian™ Sensor (3) values will be compared to YSI™* plasma glucose values during YSI™* FSTs. A within 20% mean agreement rate between Guardian™ Sensor (3) values and YSI™* plasma glucose values during YSI™* FST days will be evaluated
- Guardian™ Sensor (3) values will be compared to YSI™* plasma glucose values during YSI™* FSTs. A within 15% mean agreement rate when SG > 180 mg/dL between Guardian™ Sensor (3) values and YSI™* plasma glucose values during YSI™* FST days will be evaluated
- Guardian™ Sensor (3) values will be compared to YSI™* plasma glucose values during YSI™* FSTs. A within 40% mean agreement rate when SG > 180 mg/dL between Guardian™ Sensor (3) values and YSI™* plasma glucose values during YSI™* FST days will be evaluated

- When iCGM values are greater than 180 mg/dL, corresponding blood glucose value read less than 70 mg/dL.
- Guardian™ Sensor (3) values will be compared to YSI™* plasma glucose values during YSI™* FSTs. A within 15% mean agreement rate when SG between 70 and 180 mg/dL between Guardian™ Sensor (3) values and YSI™* plasma glucose values during YSI™* FST days will be evaluated
- Guardian™ Sensor (3) values will be compared to YSI™* plasma glucose values during YSI™* FSTs. A within 40% mean agreement rate when SG between 70 and 180 mg/dL between Guardian™ Sensor (3) values and YSI™* plasma glucose values during YSI™* FST days will be evaluated
- When iCGM values are less than 70 mg/dL, no corresponding blood glucose value shall read above 180 mg/dL.
- Guardian™ Sensor (3) values will be compared to YSI™* plasma glucose values during YSI™* FSTs. A within ± 15 mg/dL mean agreement rate when SG less than ($<$) 70 mg/dL between Guardian™ Sensor (3) values and YSI™* plasma glucose values during YSI™* FST days will be evaluated
- Guardian™ Sensor (3) values will be compared to YSI™* plasma glucose values during YSI™* FSTs. A within ± 40 mg/dL mean agreement rate when SG less than ($<$) 70 mg/dL between Guardian™ Sensor (3) values and YSI™* plasma glucose values during YSI™* FST days will be evaluated

Within each block of 16, secondary endpoints (a total of 176) will be evaluated in a fixed sequence of testing for adjustment of multiplicity. The results will be compared to the iCGM Special Control criteria for sensor accuracy (SG limit of **40-400** mg/dL). For each of the endpoints, iCGM measurement refers to the sensor glucose value:

- % of iCGM measurements that indicate a positive glucose rate of change greater than 1 mg/dL/min when the corresponding true negative glucose rate of change is less than -2 mg/dL/min as determined by the corresponding blood glucose measurements
- % of iCGM measurements that indicate a negative glucose rate of change less than -1 mg/dL/min when the corresponding true positive glucose rate of change is greater than 2 mg/dL/min as determined by the corresponding blood glucose measurements
- Guardian™ Sensor (3) values will be compared to YSI™* plasma glucose values during YSI™* FSTs. A within 20% mean agreement rate between Guardian™ Sensor (3) values and YSI™* plasma glucose values during YSI™* FST days will be evaluated
- Guardian™ Sensor (3) values will be compared to YSI™* plasma glucose values during YSI™* FSTs. A within 15% mean agreement rate when SG > 180 mg/dL between Guardian™ Sensor (3) values and YSI™* plasma glucose values during YSI™* FST days will be evaluated

- Guardian™ Sensor (3) values will be compared to YSI™* plasma glucose values during YSI™* FSTs. A within 40% mean agreement rate when SG >180 mg/dL between Guardian™ Sensor (3) values and YSI™* plasma glucose values during YSI™* FST days will be evaluated
- When iCGM values are greater than 180 mg/dL, corresponding blood glucose value read less than 70 mg/dL.
- Guardian™ Sensor (3) values will be compared to YSI™* plasma glucose values during YSI™* FSTs. A within 15% mean agreement rate when SG between 70 and 180 mg/dL between Guardian™ Sensor (3) values and YSI™* plasma glucose values during YSI™* FST days will be evaluated
- Guardian™ Sensor (3) values will be compared to YSI™* plasma glucose values during YSI™* FSTs. A within 40% mean agreement rate when SG between 70 and 180 mg/dL between Guardian™ Sensor (3) values and YSI™* plasma glucose values during YSI™* FST days will be evaluated
- When iCGM values are less than 70 mg/dL, no corresponding blood glucose value shall read above 180 mg/dL.
- Guardian™ Sensor (3) values will be compared to YSI™* plasma glucose values during YSI™* FSTs. A within ± 15 mg/dL mean agreement rate when SG less than ($<$) 70 mg/dL between Guardian™ Sensor (3) values and YSI™* plasma glucose values during YSI™* FST days will be evaluated
- Guardian™ Sensor (3) values will be compared to YSI™* plasma glucose values during YSI™* FSTs. A within ± 40 mg/dL mean agreement rate when SG less than ($<$) 70 mg/dL between Guardian™ Sensor (3) values and YSI™* plasma glucose values during YSI™* FST days will be evaluated

